11.0 TOXICITIES/SIDE EFFECTS

For non-serious adverse events, we will only be capturing the toxicities that are possibly related to protocol treatment. The National Cancer Institute (NCI) Common Terminology Criteria for Adverse Events (CTCAE) version 4.0 will be used as an instrument to evaluate toxicities, discussed in section 12.

The toxicities associated with radiation therapy to the spine or pelvis can be classified as either early (occurring within 90 days of the treatment) or late toxicities (after 90 days to 1 year). Mild acute toxicities that are expected from treatment include Grade 1-2 fatigue and irritation at the sites of catheter insertion, as well as a generally transient pain flare in the treated bone site. Less likely (<5% of the time) would be infection or bleeding at the sites of catheter insertion. Rare but serious (<1%) acute toxicities could include complications such

MEMORIAL SLOAN-KETTERING CANCER CENTER IRB PROTOCOL #: 12-260 A(4)

as perforation of a visceral organ during catheter placement (lung, bowel, or kidney) or fractures in the bones of the spine.

There are two types of toxicity which will be considered as potentially serious adverse events from the brachytherapy treatment: neurologic and musculoskeletal. These generally occur late and include myelitis or pathologic fractures of the bones of the spine and/or pelvis. Neurologic and musculoskeletal toxicities will be evaluated with the National Cancer Institute (NCI) Common Toxicity Criteria v4.0 (discussed in section 12, also see Appendix 2 for specifics). The probability of severe (\geq grade 3) neurologic and musculoskeletal toxicity is expected to be less than 10%, which is below the currently observed rate of severe toxicity reported by patients who undergo standard radiation therapy for lesions of the spine at MSKCC.

DEFINITIONS

1. Definition of an Adverse Event (AE)
 - a. An Adverse Event is defined by the GCP (Guide to Good Clinical Practice) as any undesirable experience occurring to a subject during a clinical trial, whether or not it is considered related to the investigational product(s). In this trial we will only document those AEs that are at least possibly related to protocol therapy.
2. Definition of a Serious Adverse Event (SAE)
 - a. A Serious Adverse Event is an adverse experience that:
 - i. is fatal or life-threatening
 - ii. is disabling
 - iii. results in hospitalization or prolongation of hospitalization, with the exception of an overnight admission following the procedure.
 - iv. results in a congenital anomaly or occurrence of malignancy
 - b. Any neurologic and musculoskeletal toxicity that is grade 3 or higher will be considered a serious adverse event.
3. Definition of an Unexpected Adverse Event
 - a. An Unexpected AE is an experience not previously reported (in nature, severity, or incidence) in the current Investigator's Brochure or general investigational plan.

Evaluation of SAE:

Review of the patient record including the treatment dosimetry will be undertaken by the principal investigator with the assistance of the co-principal investigator and at least one investigator from both Medical Physics and Radiology. The principal investigator may decide to continue the protocol without modification, discontinue the study altogether, or to modify the protocol prior to enrolling more patients pending the results of the review.

12.0 CRITERIA FOR THERAPEUTIC RESPONSE/OUTCOME ASSESSMENT

Review of dosimetric characteristics of the patients' treatment plans will be performed to determine if the treatments were able to adequately meet determined parameters.

The primary objective of the study is to validate the feasibility of HDR treatment of spine and pelvic lesions using catheters placed under image-guided navigational techniques:

1. This will be accomplished by the following criteria: We consider a D90 of $\geq 80\%$ for the lesion GTV with cord and/or cauda equina maximum doses ≤ 8 Gy as acceptable dosimetric endpoints. Dosimetry will be evaluated following implantation of

MEMORIAL SLOAN-KETTERING CANCER CENTER IRB PROTOCOL #: 12-260 A(4)

brachytherapy catheters and prior to patient treatment.

The secondary objectives concern toxicity and clinical outcomes, and will be evaluated regardless of whether the primary objective was met:

1. Demonstration of the safety of HDR brachytherapy for previously irradiated lesions of the spine and pelvis.
 - a. Both acute and late (1 year post-treatment) toxicity will be evaluated. Neurological evaluation and ambulation assessment will be carried out prior to treatment to serve as a baseline. During each subsequent follow up visit, patients will be asked to provide evaluations of their symptoms. The primary expected toxicities are musculoskeletal and neurological. Grade 2 toxicity is almost always self limiting and by definition manageable with medications, not requiring invasive procedures. Thus grade 2 toxicities will not be considered as serious adverse events.
2. Efficacy of HDR brachytherapy for relief of pain
 - a. Patients will be assessed prior to treatment and at each followup visit using the standardized 11-point (0-10) Numeric Rating Scale (NRS-11). Descriptive statistics regarding time to, degree of, and duration of relief from pain (if any) will be reported in summary form.
3. Disease-free progression at the treatment site.
 - a. Imaging studies and clinical assessment performed at each followup date will be used to assess degree of response; tumor control will be defined for this study as the lack of tumor progression at the treated site, where progression may consist of an increase in maximal dimension of the tumor by $\geq 20\%$, compromise of the spinal cord/cauda equina and/or exiting spinal nerves (assessed clinically or radiographically), or both.

The following instruments will be used in the evaluation of toxicities:

NCI Common Toxicity Criteria. The NCI scales are simple to complete and provide a means for assessing patient symptoms. For the purposes of this study, the musculoskeletal panel of questions will be limited to those pertaining to back pain and myositis (see Appendix 2). To evaluate neurological toxicities, the categories will be limited to cerebrospinal fluid leak and myelitis (see Appendix 2). Only the CTCAE v4.0 will be used in toxicity grading.

Numeric Rating Scale (NRS-11). The NRS-11 numeric rating scale is a validated tool for discriminating pain level, in which patients rank their "pain score" on a scale of 0 to 10, where 0 is equivalent to "no pain," and 10 is "unbearable pain." [Downie 1978, Paice 1997]

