14. BIOSTATISTICS

This is a pilot interventional study to evaluate the feasibility of high dose rate (HDR) brachytherapy using image-guided navigational techniques as salvage therapy for previously treated lesions of the spine. The primary outcome that we wish to assess is the reproducibility of the treatment plan parameters; secondary outcomes include toxicity, relief of pain, and local disease progression.

In terms of technical feasibility, a patient is regarded as being successfully treated if the target D90 is $\geq 80\%$ AND the cord/cauda max dose is 8 Gy. To this end we will enroll 20 patients and declare the procedure feasible if at least 15 patients can be successfully treated. For this decision rule we have the following probability table:

True feasibility rate	55%	60%	65%	70%	75%	80%	85%	90%
Probability of declaring feasible	0.055	0.126	0.245	0.416	0.617	0.804	0.933	0.989

We believe this procedure will be quite safe for patients; a previous study from Japan [Seichi 1999] showed serious toxicity rates of approximately 3%, and we anticipate ours will be even lower. Among the 20 patients we expect to see less than 2 adverse events. In the event that a second serious adverse event (\geq Grade 3, or as otherwise defined above in Section 11.0) occurs, this protocol will be immediately halted and the investigator will carefully examine the cases with the assistance of the co-principal investigator and at least one investigator from both Medical Physics and Radiology and review the protocol (to be either terminated or modified in order to proceed further). Self-reported pain scores will be recorded and descriptive statistics regarding time to, degree of, and duration of relief from pain (if any) will be summarized numerically and/or graphically. In-field progression-free probability will be estimated using Kaplan-Meier estimation.

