17.2 Serious Adverse Event (SAE) Reporting

Any SAE must be reported to the IRB/PB as soon as possible but no later than 5 calendar days. The IRB/PB requires a Clinical Research Database (CRDB) SAE report be submitted electronically to the SAE Office at [contact]. The report should contain the following information:

Fields populated from CRDB:

- Subject's name (generate the report with only initials if it will be sent outside of MSKCC)
- Medical record number
- Disease/histology (if applicable)
- Protocol number and title

Data needing to be entered:

- The date the adverse event occurred
- The adverse event
- Relationship of the adverse event to the treatment (drug, device, or intervention)
- If the AE was expected
- The severity of the AE
- The intervention
- Detailed text that includes the following
 - A explanation of how the AE was handled
 - A description of the subject's condition
 - Indication if the subject remains on the study
 - If an amendment will need to be made to the protocol and/or consent form.

MEMORIAL SLOAN-KETTERING CANCER CENTER IRB PROTOCOL #: 12-260 A(4)

The PI's signature and the date it was signed are required on the completed report.

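### Section 12 rules out every grade 2 toxicity as an SAE, while Section 11 defines an SAE by outcome at any grade, so a hospitalising or disabling grade 2 event could miss the 5-day report

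*Combined protocol and SAP*

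**What the plan says.** Three sections of the combined protocol and SAP bear on what counts as an SAE, and a fourth sets the reporting deadline.

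- **Section 11.0, Definitions, item 2.a.** The definition opens "A Serious Adverse Event is an adverse experience that" and lists outcomes: death or threat to life, disability, hospitalisation, and congenital anomaly or malignancy. The hospitalisation criterion is "results in hospitalization or prolongation of hospitalization, with the exception of an overnight admission following the procedure". No criterion names a CTCAE grade.
- **Section 11.0, Definitions, item 2.b.** This adds a route by grade: "Any neurologic and musculoskeletal toxicity that is grade 3 or higher will be considered a serious adverse event".
- **Section 12.0, secondary objective 1.** The reasoning is "Grade 2 toxicity is almost always self limiting and by definition manageable with medications, not requiring invasive procedures", and the conclusion is "Thus grade 2 toxicities will not be considered as serious adverse events".
- **Section 14.** The trial halts on a second SAE, described as grade 3 or higher, "or as otherwise defined above in Section 11.0".
- **Section 17.2.** "Any SAE must be reported to the IRB/PB as soon as possible but no later than 5 calendar days". The section neither defines an SAE nor points to a definition.

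Section 11.0 also provides for a case review of SAEs, including the treatment dosimetry, by the principal investigator with the co-principal investigator and investigators from Medical Physics and Radiology.

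**The concern.** Severity and seriousness are different classifications. A CTCAE grade describes how intense an event is; seriousness, as item 2.a uses it, describes what the event led to. Section 12 uses the first to decide the second.

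The reason it gives does not reach the item 2.a tests. That an event can be managed with medication and without an invasive procedure does not mean that the patient was not admitted or was not left disabled. A patient can be admitted for drug treatment alone.

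Two safeguards depend on whether an event is called an SAE and are exposed to the conflict: the 5-day report to the IRB/PB and the case review in Section 11. If staff classify events by the Section 12 sentence, a grade 2 event with a serious outcome would go through neither.

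**Working it through.** No arithmetic applies. The point concerns a definition, the plan gives no figure for it, and no sample size, power or feasibility figure depends on it. The check sets the sections side by side.

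**Step 1. Classify each kind of event under each section.**

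| Event | Section 11, item 2.a (outcome) | Section 11, item 2.b (grade) | Section 12 | Result |
|---|---|---|---|---|
| Grade 2, no item 2.a outcome | Not an SAE | Not an SAE | Not an SAE | Consistent |
| Grade 2, disabling, or hospitalised other than the excepted overnight stay | SAE | Not an SAE by this route | Not an SAE | **Conflict** |
| Grade 3 or higher, neurologic or musculoskeletal | Depends on outcome | SAE | Silent | No conflict |
| Grade 3 or higher, other type | Depends on outcome | Not an SAE by this route | Silent | No conflict |

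The conflict is confined to the second row.

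**Step 2. Does item 2.b put a grade floor under item 2.a?** No. It is a separate item that makes certain toxicities serious because of their grade. It does not say that an item 2.a outcome counts only above some grade. The one carve-out in the hospitalisation criterion concerns an overnight stay after the procedure and has nothing to do with grade.

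**Step 3. Does the document say which section prevails?** No. Neither Section 11 nor Section 12 mentions the other on this point, and there is no order of precedence.

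**Step 4. Which consequences are affected?**

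- *5-day report (Section 17.2).* It applies to any SAE and names no definition. The conflict is unresolved here.
- *Case review (Section 11).* It stands in the same section as the outcome definition, which favours that definition. An event already classed as non-serious under Section 12 would still not prompt the review.
- *Halt (Section 14).* The trigger begins "In the event that a second serious adverse event" and specifies grade 3 or higher or the Section 11 definition. Section 12 is not cited. A grade 2 event meeting item 2.a therefore counts towards the halt under the rule's own terms.
- *Stop to accrual (Section 4.1).* It is keyed to the level of grade 3 toxicity, so grade 2 events do not enter it under either reading.
- *Recording of the event.* Section 11 captures non-serious events that are possibly related to treatment. A grade 2 toxicity of that kind would still be recorded; expedited reporting and SAE review are what could be lost.

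**Step 5. How often would the second row occur?** The documents give no rate of grade 2 events that hospitalise or disable. Whether an event can be graded 2 and still have such an outcome depends partly on the CTCAE grading text in Appendix 2, which is listed but not reproduced in the text available. No frequency can be derived.

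**The case against.** The strongest reply is that the sections can be read together. Section 11 holds the formal definition. The Section 12 sentence sits under a secondary safety objective, shortly after a statement that the main expected toxicities are musculoskeletal and neurological. It can be taken as the counterpart of item 2.b: grade 2 toxicity of those types is not made serious by its grade. On that reading item 2.a is untouched, and an event of another type, such as an insertion-site infection leading to admission, lies outside the sentence altogether.

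That reading is possible and may be what was meant, but it is not written. The sentence limits itself neither to grade alone nor to particular toxicity types. Even if confined to musculoskeletal and neurological toxicity, it would still conflict with item 2.a when taken literally, because item 2.a covers those toxicities too.

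Two further points stand. The word *almost* in Section 12 qualifies only the claim that grade 2 toxicity is self-limiting; it does not concede that such events hospitalise or disable. And the set of affected events may be very small.

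A reader might also infer that the Section 12 sentence weakens the halt on a second SAE, and might try to express this as a change in the probability of halting among 20 patients. The documents do not support that. The halting rule carries its own definition, which leads to Section 11, and any such probability would need a rate of serious grade 2 events that the documents do not give. An investigator who misclassifies an event under Section 12 could fail to count it, but that would be a misapplication of Section 14 and not an effect of its wording.

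**Conclusion.** The point holds as an internal contradiction of minor severity. As written, a grade 2 event that disables or hospitalises a patient is an SAE under Section 11, item 2.a, and is not one under Section 12. Section 17.2 does not settle which classification governs, so the event could miss the 5-day report and the case review in Section 11.

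The conclusion rests on the literal text of Section 12 and on the absence of any rule of precedence. It needs no assumption about event rates. The practical size is unknown and possibly small. The halting rule, the grade-based stop to accrual, the endpoints and the sample size are not directly affected.

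**What to change.** Reconcile Sections 11, 12 and 17.2. Either delete the Section 12 sentence on grade 2 toxicity, or replace it with:

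> Grade 2 toxicity is not an SAE on grade alone; any event, whatever its CTCAE grade, that meets a Section 11 item 2.a criterion is an SAE and is reported under Section 17.2.

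Keep grade 3 or higher as the separate severe-toxicity endpoint, so that severity and seriousness are reported side by side.

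The change is one sentence. It may bring a few more SAE reports and a slightly less favourable SAE count.

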2.0 OBJECTIVES AND SCIENTIFIC AIMS

The objective of this study is to validate methods of delivering adequate conformal dose to spinal and pelvic targets with HDR catheters using image-guided navigational techniques.

The Specific Aims of this study are to:

1. Verify feasibility of HDR treatment of spinal and/or pelvic lesions using catheters placed under image-guided navigational techniques, to provide improved dosimetric coverage of lesions such that
 - a. Gross Target Volume (GTV) D90 \geq 80%
 - b. Cord/Cauda max dose (Cord/Cauda Dmax) of < 8 Gy

Secondary objectives:

1. Demonstrate safety of HDR brachytherapy for previously irradiated lesions of the spine and/or pelvis, defined as an acceptable level of severe toxicity (both acute and late effects) in the setting of HDR brachytherapy treatment. Severe toxicity will be defined as \geq grade 3 NCI CTCAE v 4.0 toxicity that is at least possibly related to treatment (see Appendix 2).
2. Assess patient pain scores referable to the treatment site using the standardized 11-point pain scale.
3. Assess patients for duration of in-field progression-free survival at the treatment site.

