8.0 PRETREATMENT EVALUATION

Any time prior to treatment start

- Review of all prior external beam radiation therapy (dose volume histograms, beam arrangement, and port films required)
- MSKCC pathology review

Within 3 months prior to treatment start

- History and physical
- KPS
- Baseline pain assessment
- Assessment of baseline comorbidities
- Conmed review

Within 30 days prior to treatment start

- CBC, Comprehensive Serum Chemistry, INR/PTT
- MRI if not otherwise contraindicated
- CT scan without contrast in the prone position (optional if supine CT already performed)
- Standard preoperative workup

Within 2 weeks prior to treatment start

- Pregnancy test for women of childbearing potential

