10.0 EVALUATION DURING TREATMENT/INTERVENTION

Dosimetric planning will be performed on pre-implantation planning CT and then merged with post-implant CT images obtained following catheter placement. Specific dosimetric parameters will include GTV V90, V100, V150, V200, D90, and cord/cauda dose volume histograms. Treatment complications will be monitored in terms of radiation related toxicity during post-procedure recovery and during followup visits; all patients treated on this protocol will be evaluated regardless of whether dosimetric goals were met.

Regular follow up visits will be scheduled at 2 months (+/- 2 weeks) and then at 3 month (+/- 2 weeks) intervals until approximately 11 months of follow up. During these follow up visits, standard evaluations currently performed on all spine and/or pelvic radiation therapy patients (physical examination and imaging) will be performed. Thus, no activities that are not currently billed will be necessary. Follow up after 1 year will be performed as per standard clinical practice with no further protocol obligations.

If after the 2 month follow up a patient is not available to come in for a follow up visit, a telephone follow up by a clinical investigator will be allowed for up to two of the remaining follow up visits. If a phone call follow up is used, the physical exam will be foregone. Outside imaging studies are also allowed but must be reviewed at MSKCC.

	Screening	Treatment	Follow up (2 months post-treatment, then every 3 months until approximately 11 months of follow up)
Review of pathology	X		
Review of prior treatment	X		
Medical history	X		
Physical Exam, including neurological assessment and ambulation assessment	X		X
KPS	X		
CBC	X		
Comprehensive Serum Chemistry	X		
INR/PTT	X		
CT spine or pelvis ¹ (without contrast)	X ²	X	X ³
MRI spine or pelvis ¹ (unless contraindicated)	X		X
Pre-operative workup	X		
AE assessment	Baseline comorbidities		X
Pain assessment	X		X
Review of Commeds	X		
Pregnancy test	X		
HDR		X	

1 Imaging location will be dependent on the lesion site of interest

2 CT scan in prone position is required unless a supine CT has already been performed within 30 days of planned treatment

3 Optional if MRI is performed

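### Minor, cheap to improve: the promised time to, degree of and duration of pain relief rest on widely spaced scores, a baseline up to 3 months old, and no required medication review after screening

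*Combined protocol and SAP*

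**What the plan says.** The secondary objective in Section 2.0 is modest: "Assess patient pain scores referable to the treatment site using the standardized 11-point pain scale". Sections 12.0 and 14 go further. Section 12.0 places pain under a heading about efficacy and states: "Descriptive statistics regarding time to, degree of, and duration of relief from pain (if any) will be reported in summary form". Section 14 repeats the commitment: "descriptive statistics regarding time to, degree of, and duration of relief from pain (if any) will be summarized numerically and/or graphically".

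The data behind these summaries are set elsewhere:

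- **Scores.** Section 12.0 has the NRS-11 taken before treatment and at each follow-up visit. Section 10.0 sets the visits: "Regular follow up visits will be scheduled at 2 months (+/- 2 weeks) and then at 3 month (+/- 2 weeks) intervals", ending at about 11 months. The nominal visits are therefore months 2, 5, 8 and 11. After month 2, up to two visits may be by telephone; then "If a phone call follow up is used, the physical exam will be foregone", and nothing else is dropped.
- **Baseline.** Section 8.0 lists the baseline pain assessment, and the medication review, under "Within 3 months prior to treatment start". It requires no repeat nearer to treatment.
- **Medication.** In the Section 10.0 schedule table the row "Review of Commeds" is marked at Screening only. The pain row is marked at Screening and Follow up.

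No section says what NRS change counts as relief, or how its start or end is dated.

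**The concern.** The schedule is enough for the objective in Section 2.0. It is thin for the three quantities promised in Sections 12.0 and 14.

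- **Timing.** A patient whose pain eases before the first visit is known only to have improved by then. Followed as written, time to relief would largely reflect the visit calendar. Section 3.3 illustrates that this can happen: in the institution's earlier series, 3 of 5 patients had relief at 1 to 4 weeks.
- **Degree.** If pain moves in either direction between an old baseline score and the procedure, that movement is counted as change after treatment.
- **Interpretation.** A lower score may go with more analgesic or steroid use. The protocol-required data cannot show whether it did.

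At stake is how far a reader can rely on a descriptive efficacy summary in a single-arm study. No test or decision depends on pain.

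**Working it through.** The plan gives no figure for pain, so there is none to reproduce. Its one computed design figure, the feasibility table in Section 14 (at least 15 of 20), matches the exact binomial at all eight entries (for example 0.8042 against the stated 0.804 at a true rate of 80%) and does not involve pain.

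**Inputs.** Visits at 2, 5, 8 and 11 months with a window of +/- 2 weeks (Section 10.0); baseline up to 3 months before treatment (Section 8.0); 20 patients (Section 14). One month = 365.25 / 12 / 7 = 4.35 weeks.

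**Nominal visits.** 2, 5, 8 and 11 months = 8.7, 21.7, 34.8 and 47.8 weeks.

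**First score after treatment.** 8.7 +/- 2 = weeks 6.7 to 10.7. Any onset before it is known only to lie between week 0 and that visit. An onset at 1 to 4 weeks would fall inside this gap.

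**Later onset or loss.** The visit interval is 3 months = 13.0 weeks. The text can be read in two ways:

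- window applied to the interval: 13.0 +/- 2 = 11.0 to 15.0 weeks;
- window applied to each nominal date: 13.0 +/- 4 = 9.0 to 17.0 weeks.

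**Duration.** Assume relief is continuous between scores that show it. The lower bound is the last visit with relief minus the first visit with relief. The upper bound is the next visit without relief minus the last time point before relief was seen, with treatment as week 0. At nominal dates:

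| Relief scored at | Not at | Lower bound (weeks) | Upper bound (weeks) |
|---|---|---|---|
| Month 2 | Month 5 | 0 | 21.7 - 0 = 21.7 |
| Months 2, 5 | Month 8 | 21.7 - 8.7 = 13.0 | 34.8 - 0 = 34.8 |

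At the extremes of the window the first upper bound becomes 21.7 + 2 = 23.7 (nominal-date reading) or 10.7 + 15.0 = 25.7 (interval reading).

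**Baseline age.** At most 3 months = 13.0 weeks before treatment. The longest gap from baseline to the first follow-up score is then 13.0 + 10.7 = 23.7 weeks. This is an outer limit; the documents give no typical baseline age.

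**Medication review.** Required at 0 of the 4 follow-up visits.

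**The case against.** The strongest reply is that this is a 20-patient feasibility pilot, that pain is secondary and descriptive, and that any outcome scored at clinic visits is known only to the visit; in-field progression has the same limit. That stands. On its own the timing point is mostly presentation; the baseline and medication points carry more weight.

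Three further replies stand in part:

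- Follow-up is standard of care (Section 4.2), so clinic charts may hold medication data. They may, but Section 10.0 describes the standard evaluations as physical examination and imaging, and no section requires medication data to be collected.
- Section 12.0 has patients evaluate their symptoms at each follow-up visit, so they could be asked when relief began. That sentence sits under toxicity, and no recalled date is planned.
- Section 8.0 already requires a preoperative workup within 30 days of treatment. It does not say that pain is scored there, so the 3-month limit stands, but it may offer a contact for a repeat score.

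A reader might infer more than the documents support. One inference is that the pain objective cannot be met; it can, because Section 2.0 asks only for scores. Another is that baselines will be 3 months old or the results biased by a known amount; neither actual age nor bias can be derived. A third is that the earlier series shows how often relief begins before month 2. Its 3 of 5 is the number reported with relief, those patients were treated without navigation, and 1 to 4 weeks may be when relief was noted. It shows only that early onset is possible.

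**Conclusion.** The point holds as a minor, inexpensive improvement. The scheduled NRS-11 scores bound onset and loss of relief but do not date them: somewhere before a first visit at weeks 6.7 to 10.7, then to within about 13 weeks. The baseline may be up to 13.0 weeks old, and required data do not link pain scores to analgesic or steroid use after screening.

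This assumes that only what the protocol requires is collected. The duration bounds also assume continuous relief between scores and some agreed definition of relief, which the plan does not give. NRS change from baseline can still be described at each visit, subject to the baseline and medication limits. The primary endpoint, the sample size and the stopping rule are unaffected.

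**What to change.** 1. **Sections 8.0 and 10.0: baseline.** Repeat the NRS-11 at a named contact close to the procedure and before anesthesia, and use that score as baseline. The preoperative workup in Section 8.0 would serve if it falls close to treatment.
2. **Section 10.0 table: medication.** Record analgesic and steroid use with the baseline score and with each follow-up score, telephone visits included. Tabulate NRS change from baseline at each visit alongside whether recorded use was higher than, the same as or lower than at baseline.
3. **Sections 12.0 and 14: reporting.** As a consequence, report NRS change by visit and describe onset and duration only as bounded by visits. If a yes/no relief status is reported, state beforehand the NRS change that defines it.

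**Cost.** One repeated question per patient (20 in all), at most 4 x 20 = 80 follow-up form lines plus one baseline line per patient, one small amendment, and a less ambitious timing summary. No visits are added. The medication record helps interpretation but cannot prove attribution in a single-arm study.

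### Section 12.0 counts cord or nerve compromise as in-field progression without requiring tumour as the cause, so a treatment injury can be scored as progression and may be left out of the severe-toxicity endpoint

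*Combined protocol and SAP*

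**What the plan says.** **Progression.** Under the third secondary objective in Section 12.0, tumour control is the absence of tumour progression at the treated site. There, "progression may consist of an increase in maximal dimension of the tumor by" at least 20%, or of "compromise of the spinal cord/cauda equina and/or exiting spinal nerves (assessed clinically or radiographically), or both". The last two words make the routes alternatives. Section 14 summarises the endpoint by Kaplan-Meier estimation.

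**Toxicity.** Section 11.0 names neurologic and musculoskeletal injury as the potentially serious toxicities: "These generally occur late and include myelitis or pathologic fractures of the bones of the spine and/or pelvis". Section 3.4 says previously irradiated patients are at increased risk of injury to the cord, cauda and exiting nerves, and Section 6.1 requires prior external beam treatment to the region. The severe-toxicity endpoint in Section 2.0 is grade 3 or higher "toxicity that is at least possibly related to treatment".

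**Capture.** Section 11.0 opens by limiting collection to possibly related toxicities for non-serious events. Its adverse event definition has no such restriction to non-serious events: "In this trial we will only document those AEs that are at least possibly related to protocol therapy". For serious events it says: "Any neurologic and musculoskeletal toxicity that is grade 3 or higher will be considered a serious adverse event". Neither that sentence nor the list of seriousness criteria mentions relatedness. Section 14 halts the protocol at the second serious adverse event. Section 17.2 requires every serious adverse event to be reported, with relationship to treatment as one item of the report.

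No section says how a single event is assigned to progression, to toxicity or to both.

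**The concern.** The structures in the neural route of the progression definition are those that Section 3.4 expects treatment to put at risk. A patient with new cord signs, no measurable growth and a myelitis caused by re-irradiation satisfies the progression wording. So does a patient whose treated vertebra fractures and compromises a nerve.

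Two secondary endpoints are exposed. In-field progression would be overstated, because a treatment injury is counted as tumour failure. Severe toxicity could be understated, because calling the event progression supplies a tumour explanation, and an event judged unrelated falls outside the Section 2.0 endpoint. With 20 patients and few events expected, one misclassified patient is visible in either result.

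**Working it through.** **1. The plan's own figures.** The plan gives no number for this point. Its one calculated table, the chance of at least 15 successes in 20, reproduces at all eight rates by the exact binomial (for example 0.8042 against 0.804 at 80%). It concerns the dosimetric endpoint and does not bear on this point.

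**2. The passages side by side.**
- Section 12.0, size route: growth of at least 20%.
- Section 12.0, neural route: compromise by itself, assessed clinically or on imaging, with no cause stated.
- Section 11.0: the serious late toxicities are myelitis and pathologic fracture.

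Myelitis is cord compromise, and a fracture can compromise a nerve or the cord. Either can meet the neural route without tumour growth. A fracture without neural compromise does not meet it.

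**3. Effect on the Kaplan-Meier estimate.** An event lowers the curve by S/n, where S is the estimate just before the event and n the number at risk. With 20 patients and no earlier censoring, S = n/20, so the step is (n/20)/n = 1/20 = 5 points. With earlier censoring, n is below 20 × S and the step is larger. For example, with S = 1 and five patients censored, it is 1/15 = 6.7 points. This is the step at the event time. The later difference depends on what would otherwise have happened to that patient.

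**4. How often the question could arise.** Section 3.4 expects neurological toxicity of about 5%. That gives 20 × 0.05 = 1 expected case and P(at least one) = 1 − 0.95^20 = 0.642. This is the chance of any such toxicity, not of a misclassified one, and Section 3.4 does not say the 5% is grade 3 or higher.

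**5. The second-event halt, as an illustration only.** Let p be the true serious rate and m the share of events lost to tumour attribution. With q = p(1 − m), P(at least 2 of 20) = 1 − (1 − q)^20 − 20q(1 − q)^19. The documents give no value for m, so it is an assumption shown over a range.

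| True rate p | m = 0 | m = 25% | m = 50% | m = 75% |
|---|---|---|---|---|
| 3% (Section 14, cited series) | 0.120 | 0.074 | 0.036 | 0.010 |
| 5% (Section 3.4) | 0.264 | 0.172 | 0.088 | 0.026 |
| 10% (Section 11.0, upper bound) | 0.608 | 0.449 | 0.264 | 0.088 |

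For p = 10% and m = 50%, q = 0.05 and 1 − 0.3585 − 0.3774 = 0.264. The 10% row is a ceiling. Section 11.0 expects less than 10% for severe neurologic and musculoskeletal toxicity combined, and some of those events, such as back pain or myositis, would not ordinarily involve neural compromise. The table applies only if an event attributed to tumour does not count toward the halt, which the documents leave unsettled.

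**The case against.** **The definition concerns tumour progression.** The governing phrase speaks of tumour progression and the wording is permissive. Imaging and clinical assessment are both used at each visit, and Section 10.0 schedules MRI unless contraindicated. A careful investigator would not call myelitis with a stable tumour progression. This is why the event can be, rather than will be, scored that way. The criterion still does not require tumour as the cause, and a clinical-only route gives no means of establishing it.

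**Progression and toxicity can coexist.** Nothing removes a progression event from the toxicity count, at least possibly related is a low bar, and Section 10.0 evaluates all treated patients for complications. This stands. Loss requires an investigator to attribute the event to tumour, and no rule guides that decision.

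**The halt.** A reader might infer that relabelling one event switches off the halting rule. The documents do not establish that. The opening of Section 11.0 confines the relatedness filter to non-serious events, and neither the serious adverse event definition, the Section 14 halt nor the Section 17.2 reporting rule sets a relatedness condition. On those passages a disabling cord event put down to tumour still counts. Only the adverse event definition in Section 11.0 points the other way.

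**Fracture.** If fracture is lost from the toxicity count, Section 12.0 offers a more direct cause: "the musculoskeletal panel of questions will be limited to those pertaining to back pain and myositis", and for neurological toxicity "the categories will be limited to cerebrospinal fluid leak and myelitis". Neither list names fracture or nerve-root injury. That is a separate weakness. The content of Appendix 2 was not available to check.

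**Stakes.** Progression is a descriptive secondary endpoint, and scoring injury as progression makes tumour control look worse, not better. Both are true, and both limit the weight of the point.

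**Conclusion.** The point holds for the progression endpoint on the text alone: a treatment injury with neural compromise and no tumour growth meets the Section 12.0 definition. Each such event costs about 5 points or more of progression-free probability at its time, assuming 20 treated patients with one evaluated site each.

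For the severe-toxicity endpoint the point is conditional. An event may be left out if it is attributed to tumour, because Section 2.0 requires relatedness.

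For the halt, the documents conflict and no conclusion can be drawn. At a true 10% rate, the chance of seeing a second event among 20 would be 0.61, 0.45, 0.26 or 0.09 with 0%, 25%, 50% or 75% of events lost. The share lost is assumed, and the figures presuppose the less favourable reading of Section 11.0. A reader might take the fall from 0.61 to 0.26 as a property of the plan, but it is not. The feasibility conclusion is untouched, because dosimetry is evaluated before treatment.

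**What to change.** **In Section 12.0:**
- Count neural compromise as progression only when imaging at that time shows tumour growth, or tumour causing the compromise. MRI is already scheduled at follow-up, with CT available where MRI is not done.
- State that progression and toxicity are not mutually exclusive. Neural compromise without imaging evidence of tumour is assessed and graded as a potential treatment toxicity, with its attribution recorded. The graded categories need a place for such an event.
- Report progression-free probability with and without events of unclear cause.

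**In Section 11.0:** reconcile the two sentences on adverse event capture with each other, with the serious adverse event definition, and with Sections 14 and 17.2. The halting threshold stays as it is.

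Deficits without radiographic growth should not all be counted toward the halt automatically. That would alter the stopping rule and could bring in deficits from unrelated causes.

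**Cost.** A few sentences and no new scheduled procedure. The toxicity figure may be slightly less favourable, and some progressions first seen clinically may be dated later, at imaging.
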